### **9.2.5 Subgroup Analysis of Efficacy Endpoint**

The response rate (centrally assessed) as the primary endpoint will be analyzed in subgroups defined by risk factors.

#### 1) Analysis Item

Response rate (centrally assessed)

#### 2) Data Handling

Background factors shown in Section [12.4 Subgroup Definitions](#) will be used as risk factors. Classification according to risk factors will be based on clinical significance or dividing the sample size into two or three nearly equal parts etc.

#### 3) Analysis Methods

The response rate (centrally assessed) and its 95% confidence intervals (Wilson) will be calculated for each subgroup. The analysis results will be summarized by squamous NSCLC and non-squamous NSCLC separately and totality.

## **10 SAFETY EVALUATION**

Unless otherwise noted, safety data to be tabulated will be those observed during the period for 28 days after the final dose (or until the start of subsequent anti-cancer therapy for non-small-cell lung cancer after the final dose, whichever comes first).

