6. Unless medically necessary, vital signs will be measured no sooner than 2 days, and other tests will be performed no sooner than 8 days after the previous measurement.
7. Perform before administering the investigational product.
8. Other than weight.
9. Perform only in Cycle 4.
10. Perform only in Cycles 2, 4, 5, 7, and 9.
11. Perform only in Cycle 3.
12. Collect sample immediately before the completion of investigational product administration.
13. Perform every cycle (every 6 weeks) between Cycle 2 and 29 and every 2 cycles (every 12 weeks) after Cycle 30.

Table 4-3 Study schedule (for subjects completing the treatment phase)

Category	Study day	At end of treatment phase ⁶	Follow-up phase	
			28 days after final dose or on discontinuation 28 or fewer days after final dose ⁶	Follow-up ⁷
Allowable range (days)		-3 to +3	-7 to +7	-
Visit		V f-0	V f-1	V f-n
Pregnancy test ¹		○ ⁸	○	
Performance Status		○	○	
Vital signs/weight/percutaneous oxygen saturation		○	○	
Chest X-ray		○	○	
12-lead ECG		○ ⁸	○	
Hematology tests, blood biochemistry tests, urinalysis		○	○	
Immunology/hormone tests		○	○	
Serum drug concentration ²		○ ⁸	○	
Anti-ONO-4538 antibody ²		○ ⁸	○	
Diagnostic imaging (e.g., CT, MRI)		○	○	○
[REDACTED]	[REDACTED]	[REDACTED]	[REDACTED]	
	[REDACTED]	[REDACTED]	[REDACTED]	
	[REDACTED]	[REDACTED]	[REDACTED]	
Concomitant drugs/adverse events ⁵		←	→	

1. Women of childbearing potential will undergo urine pregnancy testing.
2. Perform only if the subject proceeds to the follow-up phase within 1 year after the start of investigational product administration (by Cycle 9). Collect sample if possible 6 to 12 weeks after the final investigational product dose.
[REDACTED]
[REDACTED]
5. Investigate all adverse events and concomitant treatments to the completion of the final tests (other than the survey for 'determination of outcome') specified in the protocol. Beyond the completion of the final tests (other than the survey for 'determination of outcome') specified in the protocol, follow any persisting adverse event for which a causal relationship with the investigational product cannot be ruled out, adverse events that resulted in discontinuation, and the concomitant treatments associated with those events until the events resolve, improve, or are determined to be permanent or no further follow-up is necessary. And all treatment-related adverse events will be followed every 2 weeks if possible.

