#### 4.3 Criteria for Handling Evaluation Time Points

If the actual date of examination is not the protocol-specified date of examination, the examination data will be accepted, except for those from diagnostic imaging, only when they are measured within the following criteria. To count days of the treatment period, the day of the start of each cycle will be defined as Day 1. If multiple data are present within the time window of a given time point, data which are obtained at a time point nearest the specified timing of examination will be preferred. If multiple safety data are obtained before and after the specified date and the lengths of time from the specified date and time are identical, those obtained after the specified date and time will be preferred.

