##### 2. Post-treatment Follow-up Period (subjects who have terminated the treatment period)

Item	End of treatment period	Post-treatment follow-up period	
		Discontinuation at or within 28 days after the final dose	Follow-up
Time window (days)	-3 - +3	-7 - +7	-

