##### **2) Data Handling**

An adverse event is any unfavorable or unintended sign (including an abnormal laboratory finding), symptom or disease during a clinical trial, whether or not related to the investigational product. Of note, tabulation will include adverse events whose symptoms have occurred/worsened during the period from the first dose of the study drug until 28 days after the final dose (or until the start of subsequent anti-cancer therapy for non-small-cell lung cancer after the final dose, whichever comes first after the final dose). In addition, all adverse events that occur during the treatment period or the subsequent anti-cancer therapy follow-up period will be listed and reported.

All adverse events reported in this clinical study will be coded by SOC (System Organ Class) and PT (Preferred Term) using MedDRA (Current version). Treatment-emergent adverse events are those events that occur or worsen on or after the first dose of study treatment up until end of study treatment.

For the analysis of adverse events, only treatment-emergent adverse events (TEAEs) will be included in the summary tables.

In case the same adverse events in terms of SOC and PT occurs to one subject more than once, it will be considered as a single event, and the highest severity and relationship status among all events will be taken into account.

Severity of adverse events will be classified using NCI-CTCAE, and where NCI-CTCAE is inapplicable, it will be classified as grade 1 ('Mild'), grade 2 ('Moderate'), grade 3 ('Severe'), grade 4 ('Life threatening or disabling/incapacitating') or grade 5 ('Death related to adverse event') based on the maximum intensity. With respect to the relationship to study drug, 'Related' will be regarded as

related, and ‘Not related’ will be regarded as unrelated. If the relationship is unclear due to a missing, the relationship to study drug is considered as ‘Related’.

(1) Time to a Grade 3 or higher adverse event will be calculated using the following formula.

- Time to a Grade 3 or higher adverse event (days) = (date of the onset of the Grade 3 or higher adverse event, or the date of worsening to Grade 3 or higher, whichever comes first) - (the first dose date of investigational product) + 1

Data will be censored if the subject has no Grade 3 or higher adverse event at 28 days after the final dose (or at the start of subsequent anti-cancer therapy for non-small-cell lung cancer after the final dose, whichever comes first).

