##### **2) Data Handling**

Data will be analyzed as observed without imputing missing data. The analysis period of clinical laboratory evaluation is treated as well as adverse events.

Any laboratory values that fall below the detection or quantification limit will be imputed to be the detection or quantification limit. The laboratory values will be summarized by Grade, if necessary, according to the National Cancer Institute Common Terminology Criteria for Adverse Events (NCI-CTCAE) version 4.0.

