### **10.2.3 Analysis Methods**

- 1) The analysis results will be summarized by squamous NSCLC and non-squamous NSCLC separately and totality.
- 2) For laboratory values and the change from baseline as continuous quantities, summary statistics (no. of subjects, mean, standard deviation, median, minimum, and maximum) will be provided for each laboratory parameter by the time of measurement, while frequency distribution will be created for laboratory values on an ordinal scale.
- 3) Frequency distribution of abnormal laboratory values will be calculated at each time point.
- 4) A Grade shift table will be prepared for changes in hemoglobin, platelet count, white blood cell count, neutrophil count, lymphocyte count, ALT (GPT), AST (GOT), ALP, total bilirubin and creatinine from baseline to the worst value observed during the period from the first dose of the study drug until 28 days after the final dose (or until the start of subsequent anti-cancer therapy for non-small-cell lung cancer after the final dose, whichever comes first).
- 5) Frequency distribution will be calculated for subjects whose liver function test values meet any of the following criteria.
  - (1) ALT or AST > 3 times ULN (Upper Limit of Normal), 5 times ULN, 10 times ULN, 20 times ULN
  - (2) Total bilirubin > 2 times ULN
  - (3) ALT or AST > 3 times ULN and total bilirubin within 1 day > 2 times ULN
  - (4) ALT or AST > 3 times ULN and total bilirubin within 30 days > 2 times ULN
  - (5) ALT or AST > 3 times ULN, total bilirubin within 1 day  $\geq$  2 times ULN, and ALP < 2 times ULN

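### SAP 4.3 accepts post-treatment visit measurements up to 35 days after the final dose, but the SAP 10 tables stop at 28 days, so on-time measurements from Days 29 to 35 are left out

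*SAP*

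**What the plan says.** All days below are counted from the final dose; they are not cycle days.

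**When the visit may take place.** Protocol Table 4-3 and SAP Table 3-3 define V f-1 as "28 days after final dose or on discontinuation 28 or fewer days after final dose", with an allowable range of -7 to +7 days. The visit includes vital signs, SpO2, ECG, hematology, biochemistry, urinalysis, immunology and hormone tests.

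**Which examinations count.** SAP 4.3 says that when the actual date differs from the planned one, "the examination data will be accepted, except for those from diagnostic imaging, only when they are measured within the following criteria". Its table for the post-treatment period, in the column headed "Discontinuation at or within 28 days after the final dose", gives the same -7 to +7 window.

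**What is tabulated.**
- SAP 10, the general rule: "Unless otherwise noted, safety data to be tabulated will be those observed during the period for 28 days after the final dose", or a shorter time if new NSCLC therapy starts.
- SAP 10.2.2, laboratory data: "The analysis period of clinical laboratory evaluation is treated as well as adverse events". Sections 10.3.2 and 10.4.2 say the same for immunology and hormone tests.
- SAP 10.2.3 4), the Grade shift table, uses the "worst value observed during the period from the first dose of the study drug until 28 days after the final dose".
- SAP 10.5 and 10.6 (vital signs and ECG) give no period of their own, so the general rule applies.
- SAP 10.1.2, adverse events (28 days counted from the last administration): "tabulation will include adverse events whose symptoms have occurred/worsened during the period from the first dose of the study drug until 28 days after". Events outside that period are listed. Time-to-event censoring and the death count use the same 28 days.

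**What is collected.** Protocol Table 4-3, footnote 5: "Investigate all adverse events and concomitant treatments to the completion of the final tests".

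**The concern.** Two SAP sections give different answers to the same question. Take a site that holds V f-1 on Day 33 and finds a first Grade 3 ALT. The visit is compliant and 4.3 accepts the value, but the shift table, which covers ALT, ends five days before the blood was drawn.

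Hepatic, renal and thyroid laboratory changes are among the select adverse event terms in SAP Addendum 1, and a change without symptoms is found only when a sample is taken. V f-1 is the last visit at which Table 4-3 shows laboratory, hormone and ECG testing. Whether its results enter the tables depends on which permitted day the site chose. The effect runs one way: an abnormality first measured on Days 29 to 35 can be lost from the tables, never added to them.

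**Working it through.** **Step 1. Check the window rule on the SAP's own figures.** Window = nominal day + lower limit to nominal day + upper limit. Limits are from SAP Table 3-1, printed windows from SAP 4.3.

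| Nominal day | Limits | Computed | Printed |
|---|---|---|---|
| 8 | -3, +3 | 5 to 11 | 5 to 11 |
| 15 | -3, +7 | 12 to 22 | 12 to 22 |
| 29 | -6, +7 | 23 to 36 | 23 to 36 |
| 43 | -6, +7 | 37 to 50 | 37 to 50 |

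All four agree.

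**Step 2. Apply it to V f-1.** 28 - 7 = 21 and 28 + 7 = 35, so the window is Days 21 to 35. Permitted days: 35 - 21 + 1 = 15.

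**Step 3. Compare with the cut-off.** Days after Day 28: 35 - 28 = 7. Share of permitted days: 7/15 = 46.7%. With a 35-day limit for visit measurements the share is 0/15.

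**Step 4. Sort the tables by how clearly they are cut.**
- Grade shift table: certain, because 10.2.3 4) restates 28 days.
- Laboratory, immunology and hormone abnormality tables, including the liver and thyroid criteria: cut on a plain reading, because their period is tied to that of adverse events.
- Vital signs and ECG: cut only through the general rule in SAP 10.
- Adverse events: sorted by date of onset or worsening, not by visit date. An event that began by Day 28 and was reported on Day 33 is kept.

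**Step 5. Subjects affected.** The documents give no distribution of visit days, so any count is an assumption. If a share *s* of V f-1 visits falls on Days 29 to 35, all 93 planned subjects attend, and none starts new NSCLC therapy before the visit, the number affected is 93 × *s*:

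| *s* | Subjects |
|---|---|
| 0 | 0 |
| 10% | 9 |
| 25% | 23 |
| 46.7% (even spread) | 43 |
| 75% | 70 |

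These are visits affected, not abnormal findings lost.

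**The case against.** **The wording at the start of SAP 10 leaves room for exceptions.** Section 4.3 could be read as the specific rule for by-visit summaries. That is arguable for vital signs and ECG, and perhaps for by-visit laboratory summaries. It cannot rescue the shift table, which states 28 days itself. Since the SAP does not say which section governs, the two need reconciling on either reading.

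**Adverse events are barely touched.** A reader might infer that everything reported at a late V f-1 drops out. The documents do not support this: onset or worsening date decides, and later events are still listed.

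**V f-1 is not the only check.** V f-0, at the end of the treatment phase, also has laboratory, immunology and hormone tests, vital signs and chest X-ray. Many late changes may already be captured there. This stands, and it limits the loss. Chest X-ray is also not at issue, because SAP 10.1 to 10.6 plans no table for it.

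**A fixed 28-day period is a legitimate choice.** This stands for adverse events, censoring and deaths. Ending those periods at each subject's V f-1 date would give extra time at risk only to subjects who lived and attended. The objection does not carry over to measurements from a visit that the SAP itself accepts as on time.

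**The treatment-emergent rule is stricter still.** SAP 10.1.2 restricts the adverse event summary tables to treatment-emergent events and ends that definition with study treatment. Read literally, it would exclude an event starting on Day 33 whatever happens to the 28-day limit. This stands, and the fix has to deal with it.

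**Conclusion.** The conflict between SAP 4.3 and SAP 10 is real. It is certain for the Grade shift table and follows on a plain reading for the laboratory, immunology and hormone abnormality tables. Vital signs and ECG are caught only by the general rule. The size that the documents support is 7 of 15 permitted visit days.

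Two stronger conclusions are tempting. One is that about 43 of 93 subjects lose their post-treatment visit; that needs an even spread of visits, full attendance and no earlier new therapy, none of which the documents state. The other is that late toxicity is substantially undercounted. V f-0 testing, the onset rule and the listing all argue against assuming that. The primary efficacy endpoint is unaffected.

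**What to change.** 1. In SAP 10, 10.2.2, 10.2.3 4), 10.3.2, 10.4.2, 10.5 and 10.6, state that measurements from a V f-1 visit inside its allowed range (at most 35 days after the final dose) are tabulated. Keep the cut-off at the start of subsequent NSCLC therapy.
2. For adverse events, time-to-event censoring and deaths, keep one fixed period for every subject: 28 days for the main tables, with a fixed 35-day table as a supplement.
3. Reconcile the treatment-emergent definition in 10.1.2 with that period, so that the summary tables have a single end date.

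The cost is SAP wording, one date flag and one supplementary table, with no new visits or data. Laboratory abnormality counts may become slightly less favourable. If adverse event collection closes at V f-1, an on-time visit can end it as early as Day 21, so the 35-day table should note that ascertainment to Day 35 is not complete for every subject.

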### **10.1 Adverse Events**

#### **10.1.1 Analysis Set**

Analysis will be performed in SAF.

#### **10.1.2 Analysis Items and Data Handling**

##### **1) Analysis Items**

- (1) Overall adverse events, adverse drug reactions and number of deaths.
- (2) Classification of adverse events

##### **2) Data Handling**

An adverse event is any unfavorable or unintended sign (including an abnormal laboratory finding), symptom or disease during a clinical trial, whether or not related to the investigational product. Of note, tabulation will include adverse events whose symptoms have occurred/worsened during the period from the first dose of the study drug until 28 days after the final dose (or until the start of subsequent anti-cancer therapy for non-small-cell lung cancer after the final dose, whichever comes first after the final dose). In addition, all adverse events that occur during the treatment period or the subsequent anti-cancer therapy follow-up period will be listed and reported.

All adverse events reported in this clinical study will be coded by SOC (System Organ Class) and PT (Preferred Term) using MedDRA (Current version). Treatment-emergent adverse events are those events that occur or worsen on or after the first dose of study treatment up until end of study treatment.

For the analysis of adverse events, only treatment-emergent adverse events (TEAEs) will be included in the summary tables.

In case the same adverse events in terms of SOC and PT occurs to one subject more than once, it will be considered as a single event, and the highest severity and relationship status among all events will be taken into account.

Severity of adverse events will be classified using NCI-CTCAE, and where NCI-CTCAE is inapplicable, it will be classified as grade 1 ('Mild'), grade 2 ('Moderate'), grade 3 ('Severe'), grade 4 ('Life threatening or disabling/incapacitating') or grade 5 ('Death related to adverse event') based on the maximum intensity. With respect to the relationship to study drug, 'Related' will be regarded as

related, and ‘Not related’ will be regarded as unrelated. If the relationship is unclear due to a missing, the relationship to study drug is considered as ‘Related’.

(1) Time to a Grade 3 or higher adverse event will be calculated using the following formula.

- Time to a Grade 3 or higher adverse event (days) = (date of the onset of the Grade 3 or higher adverse event, or the date of worsening to Grade 3 or higher, whichever comes first) - (the first dose date of investigational product) + 1

Data will be censored if the subject has no Grade 3 or higher adverse event at 28 days after the final dose (or at the start of subsequent anti-cancer therapy for non-small-cell lung cancer after the final dose, whichever comes first).

(2) Time to a Grade 3 or higher adverse drug reaction will be also calculated in the same manner.

(3) Select adverse events will be defined as adverse events to be coded as PTs in any of the categories specified in [Addendum 1 List of Select Adverse Events](#) (i.e., Endocrine Adverse Events, Hypersensitivity/Infusion Reactions, Gastrointestinal Adverse Events, Hepatic Adverse Events, Pulmonary Adverse Events, Renal Adverse Events and Skin Adverse Events).

Time to a select adverse event will be calculated by category using the following formula.

- Time to select adverse event (days) = (date of the onset of the earliest select adverse event in the category) – (the first dose date of investigational product) + 1

Data will be censored if the subject has no select adverse event in any of the categories at 28 days after the final dose (or at the start of subsequent anti-cancer therapy for non-small-cell lung cancer after the final dose, whichever comes first).

(4) Time to select adverse drug reaction will be also calculated in the same manner.

(5) Number of deaths

The number of deaths will be defined as the total number of subjects who have died during the period from the first dose of the study drug until 28 days after the final dose (or until the start of subsequent anti-cancer therapy for non-small-cell lung cancer after the final dose, whichever comes first).

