### **10.1.3 Analysis Methods**

1) Overall Adverse Events, Adverse Drug Reactions and Number of Deaths

(1) The analysis results will be summarized by squamous NSCLC and non-squamous NSCLC separately and totality.

- (2) The number of subjects (incidence rate) of the overall incidence will be provided for all adverse events and adverse drug reactions). The data will be displayed as “subject number (incidence of subjects (%))”.
- (3) The numbers of deaths, subjects with Grade 3 or higher adverse events and adverse drug reactions, and serious adverse events and adverse drug reactions, and discontinuations due to adverse events and adverse drug reactions, and adverse events and adverse drug reactions led to death will be summarized.

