## 2) Classification of Adverse Events

- (1) The analysis results will be summarized by squamous NSCLC and non-squamous NSCLC separately and totality.
- (2) Adverse events and adverse drug reactions will be summarized by SOC, PT and CTCAE grade (grade 1, 2, 3, 4, and 5). The data will be displayed as “subject number (incidence of subjects (%))”.
- (3) Incidences of adverse events and adverse drug reactions by SOC and PT will be summarized. In addition, incidences of adverse events and adverse drug reactions will be summarized by SOC, PT and CTCAE grade (any grade, grade 3 or 4, grade 5). And adverse events and adverse drug reactions with an incidence at or above a certain level will be summarized by SOC, PT and CTCAE grade (any grade, grade 3 or 4, grade 5).
- (4) Incidences of adverse events and adverse drug reactions leading to death will be summarized by SOC and PT.
- (5) Incidences of adverse events and adverse drug reactions leading to discontinuation of the study treatment will be summarized by SOC, PT and CTCAE grade (any grade, grade 3 or 4, grade 5).
- (6) Incidences of adverse events and adverse drug reactions leading to interruption of the investigational product will be summarized by SOC, PT and CTCAE grade (any grade, grade 3 or 4, grade 5).
- (7) Incidences of serious adverse events and adverse drug reactions will be summarized by SOC, PT and CTCAE grade (any grade, grade 3 or 4, grade 5).
- (8) Incidences of select adverse events and adverse drug reactions will be summarized by categories, PT and CTCAE grade (any grade, grade 3 or 4, grade 5).
- (9) Incidences of select adverse events and adverse drug reactions leading to discontinuation will be summarized by categories, PT and CTCAE grade (any grade, grade 3 or 4, grade 5).
- (10) Incidences of serious select adverse events will be summarized by categories, PT and CTCAE grade (any grade, grade 3 or 4, grade 5).

(11) Kaplan-Meier curves will be presented for time to onset of select adverse events and adverse drug reactions. Kaplan-Meier curves will also be displayed for time to onset of Grade 3 or higher adverse events and adverse drug reactions.

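### SAP 10.1.2 sets two different adverse event windows for the same summary tables and does not say which one governs

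*SAP*

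**What the plan says.** The SAP states the 28-day window in several places:

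- The opening of section 10 sets it as the default: "safety data to be tabulated will be those observed during the period for 28 days after the final dose", cut short by the start of subsequent lung cancer therapy. The sentence allows for exceptions noted elsewhere.
- Section 10.1.2, 2) Data Handling, applies it to adverse events. Tabulation covers events that occurred or worsened "during the period from the first dose of the study drug until 28 days after the final dose", with the same cut at subsequent therapy.
- Section 10.1.2, 2) (1) to (4), censors time to Grade 3 or higher events and time to select events at the same point.
- Section 10.1.2, 2) (5), counts subjects "who have died during the period from the first dose of the study drug until 28 days after the final dose".
- Section 10.2.3, 4), builds the laboratory grade shift table on the "worst value observed during the period from the first dose of the study drug until 28 days after the final dose".

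The second paragraph of the same Data Handling text in 10.1.2 gives another rule. Treatment-emergent events are those that "occur or worsen on or after the first dose of study treatment up until end of study treatment", and "only treatment-emergent adverse events (TEAEs) will be included in the summary tables".

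The tables that pass through this filter are in section 10.1.3. They include the overview, where "adverse events and adverse drug reactions led to death will be summarized" appears in the same item as the number of deaths, and the table described by "Incidences of adverse events and adverse drug reactions leading to death will be summarized by SOC and PT".

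**The concern.** The two rules in 10.1.2 apply to the same outputs but can stop on different days. The second rule stops at the end of study treatment, which neither document defines, and no sentence says which rule prevails. The programmer's reading would therefore decide which events enter the main safety tables.

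If the treatment-emergent rule is followed as written, events starting after treatment but within 28 days of the last dose drop out of the incidence, serious event and fatal event tables. Some events leading to discontinuation could drop out too. The death count and the time-to-onset curves would still cover those days. An event could then appear in a Kaplan-Meier curve and be absent from the matching incidence table. Safety is half of the study objective, so its main tables should not depend on an unstated choice.

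**Working it through.** The SAP states no figure to reproduce here. The check compares the texts and then measures the gap in days.

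**Possible meanings of the end of study treatment.** Three anchors in the SAP could supply a date. None is linked to the treatment-emergent definition.

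1. The final dose date, which ends the duration of treatment in section 7.2.
2. The end-of-treatment-period visit in section 4.3, item 2, listed in a separate column from the 28-day visit.
3. The Day 43 visit of the cycle, with an allowed range of Days 37 to 50 (Table 3-1, note 6).

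**Inputs.** Dosing every 14 days (SAP 3.4) and a window running to 28 days after the last dose (SAP 10 and 10.1.2). Assumptions: dosing on schedule, no subsequent therapy and no death before the window closes.

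**Formulas.** For k doses, the last dose falls on day L = 1 + 14(k − 1). The full window is W = L + 28 days. If treatment ends at L, 28 days fall outside the treatment-emergent window. If it ends at L + 14, 14 days fall outside.

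| Doses k | L | W | Lost if end is L | Lost if end is L + 14 |
|---|---|---|---|---|
| 1 | 1 | 29 | 28/29 = 97% | 14/29 = 48% |
| 3 | 29 | 57 | 28/57 = 49% | 14/57 = 25% |
| 6 | 71 | 99 | 28/99 = 28% | 14/99 = 14% |
| 27 | 365 | 393 | 28/393 = 7% | 14/393 = 4% |

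**Visit range after three doses.** Ending on Day 37 leaves out 57 − 37 = 20 days (20/57 = 35%). Ending on Day 50 leaves out 57 − 50 = 7 days (7/57 = 12%).

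**Opposite direction.** SAP 3.6, criterion 6, ends treatment when dosing is delayed by more than 6 weeks. Counting 42 days from the last dose puts the end at about L + 42, which is 42 − 28 = 14 days beyond W. Counting from the next due dose gives L + 14 + 42 = L + 56, which is 56 − 28 = 28 days beyond W. In that case the treatment-emergent window is the longer one.

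**Zero case.** If the end of study treatment is taken as L + 28, nothing is lost, but the SAP does not say this.

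**Worked example.** A third dose is given on Day 29. A fatal event starts on Day 54, which is 25 days later, with no subsequent therapy and death by Day 57. The death is counted, because the window runs to Day 57. The event is outside the treatment-emergent window whether treatment ended on Day 29, 43 or 50. The deaths line and the fatal-event line of the same overview would then disagree.

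**The case against.** The strongest reply is that 28 days is plainly intended. It is the default for section 10, is repeated across the safety analyses and is written in the same subsection as the treatment-emergent sentence. The revision history shows the section 10 default being added in SAP version 2.0 so that safety would be evaluated properly. On this view the fault is one loose phrase and not a rival window. The intent is probably as described, and it supports the choice of fix. It does not settle precedence: the section 10 default gives way to anything noted elsewhere, and the restriction of summary tables to treatment-emergent events is explicit and specific. A programmer who applied it literally would be following the SAP.

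Other points stand in part:

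- The 97% figure comes from the narrowest reading and a single dose. The share falls to 7% or 4% after 27 doses and to zero if the end means 28 days after the last dose.
- All shares are calendar days, not events.
- Events leading to discontinuation usually start before the decision to stop, so that table is exposed mainly under the last-dose reading.
- The death count is not limited to deaths from adverse events, so it can differ legitimately from the fatal-event line. The example needs onset, not only death, after the end of treatment.
- All adverse events are still listed, so no data are lost.

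These points limit the size of the problem. They do not remove the conflict.

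**Conclusion.** The concern holds and should be fixed. SAP 10.1.2 contains two incompatible rules for the adverse event summary tables, one of them with an undefined end. The difference is 28 days per subject if treatment ends at the last dose and 14 days if it ends one dosing interval later. It can run 14 to 28 days the other way after a long hold. The losses are upper bounds, since the window also closes at subsequent therapy or death, and they assume on-schedule dosing. The relative effect is largest for subjects who stop early. The number of events affected cannot be derived from the documents. The primary endpoint, the listings and the grade shift table are not affected.

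**What to change.** In SAP 10.1.2, define a treatment-emergent event as one with onset or worsening from the first dose to 28 days after the final dose, or to the start of subsequent lung cancer therapy if earlier. Use that single window for the adverse event tables, the death count and the time-to-onset analyses.

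In the same edit, correct a minor wording point in 10.1.2, 2) (3). Time to a select event is calculated separately for each category, but the censoring sentence refers to having no event in any category. It should refer to no select event in the category being analysed.

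The cost is SAP wording and derivation flags; no new data are needed. Reported event rates may be higher than in tables cut at the end of treatment, by an amount that the documents do not allow one to estimate.
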